Sixty percent of Canadian adults are accessible through the workplace (Government of Canada; Employment and Social Development). Thus, workplace wellness programs that include physical activity components provide a viable option to encourage employees to become more physically active. Recent studies have demonstrated that workplace wellness programs significantly improve the health status of lean as well as obese individuals⁵ with hypertension, dyslipidemia and psychological distress.⁶ Despite this information, many workplaces do not want to intrude into employee's personal lives or incur significant costs as a result of implementing evidence-based programming. In a previous study conducted by our group entitled ENCOURAGEing Workplaces, we successfully supported 54 workers to increase their total physical activity levels by 160 minutes per week through an individualized approach to physical activity prescription. This outcome stimulated our team to identify strategies to upscale the ENCOURAGE approach to influence the health behaviour of a larger number of Manitobans. Moving forward with the ENCOURAGE health promotion model, we will use *mobile health technology* to support employees to become more physically active, while offering employers a solution that can be easily implemented in a variety of contexts. We recognize the technical challenge of creating a physical activity promotion mobile application (herein referred to as the ENCOURAGE App) that is tailored for the workplace sector. Therefore, we have partnered with Tactica Interactive (<http://tactica.ca/>) to secure the programming expertise necessary to develop the app (**Appendix 1**). Tactica staff have helped us to refine the app concept and have developed a two-page description of the ENCOURAGE app that is included within this document (**Appendix 2**). Our research team previously conducted the ENCOURAGEing Workplaces project (E2014: 094) at this site and have the support of the St. Boniface Hospital executive (**Appendix 3**) and union leadership (**Appendix 4**) to conduct this new project. For the development phase of this App, we have conducted a market research survey (H2015:405) to inform the user development of a prototype version of the App, completed the testing of a proto. We are also testing the prototype version of the ENCOURAGE App in a user observation setting (H2016:097) to determine the user experience and what they liked and disliked with the App, and beta tested the App to further develop the final product. The present study will publicly release the final ENCOURAGE App product.

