- 2) The recruitment of a sub-sample of 60 participants who live in Winnipeg, MB which will be drawn from the larger sample of 300 participants and by advertisement. In addition to completing all the components listed above from the recruitment of 300 participants, they will be also asked to wear a physical activity monitor, called an accelerometer.

Inclusion and exclusion criteria

Inclusion criteria:

- Male and female employees 18-70 years old
- Self-identify as being physically inactive in the last 3 months (less than 150 minutes of moderate-vigorous physical activity per week)
- Ready to adopt a more physically active lifestyle based on the Transtheoretical Model¹⁰
- Specific to the sub-sample of 60 participants: Live in Winnipeg, MB

Exclusion criteria:

- Individuals who do not have a personal mobile phone
- Any physical limitations that would not allow a person to engage in physical activity
- Any cognitive limitations that would not allow a person to consent for the study
- Specific to the sub-sample of 60 participants: Those who live outside of Winnipeg, MB.

To our knowledge, no characteristics of the participants make them especially vulnerable or require extra precautions to administer the user observation study. Participants will be healthy volunteers able to provide informed consent.

Participant recruitment

Recruitment of participants involves two phases (Figure 1):

- 1) Recruitment of 300 individuals who download the ENCOURAGE App the iTunes Store or Google play and choose to enroll in the study. Users will be asked via a textbox to determine if they wish to participate in a research project. A description of the project, as well as an electronic consent form will be provided prior to enrolment through Survey Monkey. In order to track participants in the study, we will be asking for their e-mail addresses, their date of birth, and first and last name initials.

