- 2) Recruitment of 60 individuals who live in Winnipeg, MB to wear an accelerometer. We will employ a convenience sampling approach, where participants who are already using the App and participating in the study (i.e., the 300 participants described above) will be asked to participate if they live in Winnipeg. Additionally, we will employ a convenience sampling approach at the St. Boniface Hospital, University of Manitoba, and Tactica Interactive. Participants will be contacted via e-mail. First, we will use an e-mail approach to contact participants. The e-mail approach will provide contact information for potential participants to reach research staff to facilitate the recruitment and consent of participants at a mutually agreeable location. Secondly, we will use a poster advertisement approach (**Appendix 7**) to facilitate recruitment. Posters will be placed around the St. Boniface Hospital, University of Manitoba, and Tactica Interactive. In total for the sub-study, more than 12,000 staff members at the St. Boniface Hospital, 8,700 faculty/staff, at the University of Manitoba, and Tactica Interactive will be accessible, including:
 - Nurses and Nurse Practitioners;
 - Physicians;
 - Property Management (electrical, carpentry, mechanical);
 - Administrators and clerical support staff; and,
 - Researchers
 - Software developers

Study procedures

Large study procedures:

After participants choose to participate in the study, participants will be asked to complete a series of questionnaires at baseline, one week and every month for a total of six months (i.e., 8 different

occasions). The questionnaires (**Appendix 8**) will take approximately 30-45 minutes to complete and comprise of the following:

- 1) Demographics
- 2) Depressive symptoms with the Patient Health Questionnaire-9
- 3) Physical activity using the Godin Leisure Time Exercise Questionnaire
- 4) Cardiovascular health risk using the Cardiovascular Health in Ambulatory Care Research Team (CANHEART) questionnaire
- 5) Occupational Sitting with the Occupational Sitting and Physical Activity Questionnaire
- 6) Self-efficacy levels for physical activity and reducing sedentary time with the Exercise Self-Efficacy Questionnaires and Self-Regulatory Efficacy to Manage Sedentary Behavior questionnaire
- 7) Confidence levels for reducing sedentary behaviors with the Barrier Self-Efficacy to Reduce Sedentary Behavior and Self-efficacy to Reduce Total Daily Sedentary Time questionnaires.

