Appendix 7: Poster advertisement

ENCOURAGE Researchers need your help!!!

Sedentary behaviour is becoming increasingly common in the modern working environment. This is concerning, as researchers are beginning to recognize that sitting for extended periods of time increases your risk of diabetes, cardiovascular disease and other adverse health outcomes. Unfortunately, sitting at work is often unavoidable, but we want you to help us change that!

We are seeking volunteers for a research study to test the public release of a mobile app that is designed to decrease sedentary time in the workplace

Are you?

[figure not shown]
- Between the ages of 18 and 70
- An employee of the University of Manitoba or St. Boniface Hospital with a fairly inactive job?
- Consider yourself physically inactive but ready to make a change towards a more active lifestyle?

If you are eligible, seven study visits will be scheduled over 6 months that will include:

- Installing the ENCOURAGE App on your mobile phone (first visit only)
- Wearing a device called an accelerometer to measure your physical activity behavior
- Complete a series of questions regarding your lifestyle behaviors and cardiovascular health risk

You will also be asked to complete weekly questions regarding your experience with the App

If you are interested, please contact us at [contact].

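### The App developer's staff are a recruitment source for the accelerometer sub-study and earlier App users are not excluded, so the uncontrolled change may be biased in either direction

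*Protocol*

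**What the plan says.** - **Who builds the App.** The protocol's background says the company was engaged "to secure the programming expertise necessary to develop the app".
- **Where the sub-study recruits.** Participant recruitment, item 2, describes a "convenience sampling approach at the St. Boniface Hospital, University of Manitoba, and Tactica Interactive" and adds: "Posters will be placed around the St. Boniface Hospital, University of Manitoba, and Tactica Interactive". The list of accessible staff ends with "Software developers". Item 2 also draws on large-study participants who are App users already.
- **Who is kept out.** There are four exclusions. The first is "Individuals who do not have a personal mobile phone"; the others are a physical limitation, a cognitive limitation and, for the sub-sample, residence outside Winnipeg. None concerns employer or earlier App use.
- **Earlier exposure.** The background states: "We are also testing the prototype version of the ENCOURAGE App in a user observation setting". It also says that the team "beta tested the App to further develop the final product". It does not say who the testers were.
- **What the sub-study is for.** The protocol's Sample Size section places the primary outcome, change in moderate-vigorous physical activity, in these 60 people. The SAP names sedentary breaks at 1 month as primary and gives no sample.
- **The poster.** Appendix 7 asks for "An employee of the University of Manitoba or St. Boniface Hospital with a fairly inactive job". It does not mention the developer.

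Neither document plans an analysis by employer or by prior App use.

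**The concern.** This is a single-group before-and-after study. No comparison arm exists to subtract an effect that has nothing to do with the App, so whatever moves the 60 participants between baseline and follow-up is read as the App's effect.

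Two groups are a problem in such a design. Employees of the developer know the product, have an interest in its success and cannot be blinded; they may move more while wearing the monitor. People who have already used the App, in an earlier version or in the current release before joining the sub-study, may start from a baseline that includes part of the benefit. The first mechanism inflates the change and the second shrinks it.

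Neither may be separable afterwards. Appendix 6 says that usage analytics are held only in aggregate and are not tied to identified individuals, so they cannot show who used the App before baseline. The items of the demographics form are not shown, so it cannot be told whether employer is asked.

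**Working it through.** **Inputs (protocol, Sample Size).** Before: mean 72, SD 64 min/week. After: mean 92, SD 86. Difference 20. Correlation 0.8. Two-sided alpha 0.05, power 80%, stated n = 44, recruited n = 60.

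**1. The plan's own figure.**

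SD of change = √(64² + 86² − 2 × 0.8 × 64 × 86) = √(4096 + 7396 − 8806.4) = √2685.6 = 51.8.

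n = (1.960 + 0.842)² × 2685.6 / 20² = 52.7, so 53 by the normal formula, or 55 with the t distribution. The stated 44 is not reproduced; it is approached only by departing from a stated input (one-sided alpha gives 42 or 43; a single average SD of 75 gives 45). That is a separate matter, and nothing below depends on 44. Power on the stated inputs (t distribution) is 0.71 at n = 44 and 0.84 at n = 60.

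**2. Insiders.** The documents give no number of developer staff, so both the count and the excess are assumptions. If k of 60 people gain an extra e min/week for reasons other than the App, the mean shifts by k × e / 60. The last column is the chance of a significant two-sided result when the true change in everyone else is zero. It uses SD √(51.8² + p(1 − p)e²) with p = k/60.

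| k | e (min/week) | Shift in mean (min/week) | Chance of significance |
|---|---|---|---|
| 3 | 20 | 1.0 | 0.052 |
| 3 | 40 | 2.0 | 0.060 |
| 6 | 20 | 2.0 | 0.060 |
| 6 | 40 | 4.0 | 0.088 |
| 12 | 20 | 4.0 | 0.090 |
| 12 | 40 | 8.0 | 0.20 |

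**3. Prior exposure.** Assume that a share q already had the full 20 min/week gain at baseline and changes no further. The mean change is then 20 × (1 − q), with SD √(51.8² + q(1 − q) × 20²).

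| q | Mean change (min/week) | Power at n = 60 |
|---|---|---|
| 0 | 20 | 0.84 |
| 10% | 18 | 0.75 |
| 20% | 16 | 0.64 |

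The activity limit at entry does not remove such people on average: 72 + 20 = 92 min/week is still below the self-reported limit of 150.

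**4. Both together**, for non-overlapping groups and a true change of 20:
- 6 insiders at +40 with 20% exposed: +4 − 4 = 0.
- 12 at +40 with 10% exposed: +8 − 2 = +6.
- 3 at +20 with 20% exposed: +1 − 4 = −3.

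The sign of the net bias depends on numbers that the documents do not contain.

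**5. Recruitment pool without the developer.** 12,000 + 8,700 = 20,700 staff, and the hospital figure is given as a minimum. Sixty is about 0.3% of that (60 / 20,700), before eligibility.

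**The case against.** The best reply is that the effect is probably small. A handful of developer employees among 60 barely moves the result: 3 at +20 raise the chance of a false positive from 0.05 to 0.052. The outcome comes from an accelerometer, which limits misreporting. The lack of a control group and the protocol–SAP disagreement on the primary outcome are larger problems, and recording employer and prior use with a sensitivity analysis might serve as well as exclusion.

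Much of this stands. The insider effect is small when insiders are few. But the protocol sets no cap on them, and an accelerometer does not stop a motivated person from moving more. A sensitivity analysis needs the information to be collected, which is not planned. Exclusion is simpler and costs almost nothing here.

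Three stronger readings are tempting, and the documents do not support them:

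- *That the recruitment plan biases the study towards success.* This is plausible for developer staff. For earlier users the likelier effect on a change score is dilution, although enthusiasts who volunteer could push the other way.
- *That it is unclear whether developer staff may enter.* The recruitment section plainly includes their company, and eligibility is set by the criteria, not by an advertisement. The poster is a wording mismatch.
- *That participants in the team's earlier hospital project, or the beta testers, are known contaminated cases.* The earlier project used individualized activity prescription, not the App, and the beta testers are not identified.

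**Conclusion.** The point holds as a possible bias of unknown net direction and size. The developer's workforce is a stated recruitment source for the sample that carries the protocol's primary outcome. Nothing excludes those employees or earlier App users, and the design has no comparator to absorb the consequence. Whether the same sample carries the SAP's primary outcome is not stated.

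Over the assumed ranges, insiders add 1 to 8 min/week to a target of 20, and prior exposure of 10% to 20% removes 2 to 4 min/week and takes power from 0.84 to between 0.75 and 0.64. These figures rest on the protocol's SDs and correlation, on a paired comparison of two occasions, on 60 complete participants, and on assumed counts and gains. They show that the issue could matter, not that it will. It is an avoidable weakness, worth correcting because correction is cheap; it is not fatal to the study.

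**What to change.** 1. In Participant recruitment, item 2, remove the developer company as a sampling and poster site. The software-developer entry in the staff list is not tied to one employer, so it can stay if it also describes staff elsewhere.
2. Add an exclusion for employees of the developer and for anyone who used a prototype or beta version of the App.
3. Take the accelerometer baseline before first App use. For sub-study members drawn from current users, where this is not possible, record the date of first use and extent of use at enrolment.
4. If any such people are already enrolled, record their employer and prior use, report the primary analysis without them and show their results separately. Both are fixed at baseline, so the rule can be written before outcome data are examined.
5. Reconcile the recruitment section with the Appendix 7 poster.

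**Cost.** One criterion, one edited paragraph, two enrolment questions and a slightly smaller pool, with more than 20,700 staff left. If people already enrolled are set aside and not replaced, power on the protocol's inputs is 0.80 at 55 and 0.79 at 53, before dropout; replacing them avoids that loss. Measuring before first use narrows the current-user route, and recording prior use is the fallback.

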
Trial objectives and purpose

The objectives of this study are to determine if the final product ENCOURAGE App can over a 6 month period:

- 1) Enhance physical activity levels; and,
- 2) Improve cardiovascular health risk;

Trial design

The public release of the ENCOURAGE App will involve two phases (Figure 1):

- 1) The recruitment of 300 individuals through the App. Any user will be able to download the ENCOURAGE App through the iTunes Store or Google Play. Note that when participants download the App, they are not automatically enrolled in the study. Participants will be prompted, after downloading the App, with a brief description of the study, as well as a pre-screening tool will be used to determine eligibility (see below for inclusion/exclusion criteria). Users will be asked via a textbox to determine if they wish to participate in a research project. Users will be asked to participate in a *time series quasi-experimental design* study to determine if the ENCOURAGE App can support participants to increase their physical activity levels over a 6 month period. The App uses a time management technique (i.e., Pomodoro technique) as a strategy to provide prompts for users to engage in an activity. The App can be customized by the users to set prompts at intervals that fits into their schedule. For example, these activities can range from a stretching activity (e.g., a neck stretch), a standing activity (e.g., stand and read), or a physical activity (e.g., fill up the printer with paper, do a squat). Additionally, the App will use Behavior Change Techniques as a way to support participants as they reduce their sedentary behavior and improve their physical activity levels.⁷ The App uses a series of Behavior Change Techniques shown to be effective in promoting a more physically active lifestyle.^{8,9} Users will also provide feedback regarding the App using an *experience sampling approach*, which uses a list of questions to guide user feedback (**Appendix 5**). Additionally, we will use *Flurry Analytics* (<http://www.flurry.com/>) to measure, track, and analyze the ENCOURAGE App performance, and aggregate-level user activity within the App. Specifically, we wish to determine the number of user sessions within the App, frequency of use, session length, user events, technical data and errors, and user geographic distribution. For a more detailed description of the experience sampling and Flurry Analytics approaches, see **Appendix 6**.

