- 8) Physical activity levels at the workplace with the Workplace Sitting Breaks Questionnaire

Research participants will be prompted within the App to a hyperlink to complete the research questionnaires on Survey Monkey. In order to track individual research participant responses The links are as follows:

- 1) Description of the study/eligibility form, consent to participate, and baseline questionnaire: <https://www.surveymonkey.com/r/L3KDHRQ>
- 2) 1 week survey: <https://www.surveymonkey.com/r/L39CZB5>
- 3) 1 month survey: <https://www.surveymonkey.com/r/L3J2M67>
- 4) 2 month survey: <https://www.surveymonkey.com/r/L3SKXGH>
- 5) 3 month survey: <https://www.surveymonkey.com/r/L3MDLCF>
- 6) 4 month survey: <https://www.surveymonkey.com/r/L3FLMWG>
- 7) 5 month survey: <https://www.surveymonkey.com/r/L3B28KX>
- 8) 6 month survey: <https://www.surveymonkey.com/r/L3P9FGC>

[figure not shown]
Participants will also be asked on two separate occasions over the 6 month period to document their experiences using an experience sampling approach. A list of questions used are in **Appendix 5**.

Sub-study procedures:

Participants from Winnipeg, MB who choose to enroll in the sub-study will complete the study procedures for the large study and will also be asked to meet with research staff to obtain consent for the smaller study and will be asked to wear an accelerometer for 7-day periods at baseline and every month for 6 months (i.e., 7 different occasions). The research appointments will last approximately 30 minutes each.

See below for a figure overviewing the flow of the study.

Figure 1. Study flow chart

Assessment of Safety

Since this is not a drug study, rescue medication is not warranted. Should any participant experience adverse effects as a consequence of participation in the study, they will be excluded from the study and receive routine clinical care. All serious adverse events as well as death due to any cause or cardiovascular death will be reviewed by the medical monitor within 24 hrs of becoming aware of events. Any Serious Adverse Events will be reported to the University of Manitoba Health Ethics Boards and St. Boniface Hospital.

Statistics

Sample Size

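### Outside the sub-study, the only described route to the follow-up surveys is a prompt inside the App, so questionnaire changes up to six months are likely to over-represent people who keep using it

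*Protocol*

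**What the plan says.** - **Aim and size.** Protocol, Trial design, item 1 plans "The recruitment of 300 individuals through the App" in order to "determine if the ENCOURAGE App can support participants to increase their physical activity levels over a 6 month period". Cardiovascular health risk is the second study objective.
- **Schedule.** Under Large study procedures, "participants will be asked to complete a series of questionnaires at baseline, one week and every month for a total of six months": eight occasions, seven of them after baseline. Activity is measured with the Godin questionnaire and cardiovascular risk with the CANHEART questionnaire.
- **Route.** The same section states: "Research participants will be prompted within the App to a hyperlink to complete the research questionnaires on Survey Monkey". It then lists a fixed web link for each occasion.
- **Contact details.** Under Participant recruitment, "we will be asking for their e-mail addresses", together with date of birth and initials, for tracking. E-mail is otherwise mentioned for sub-study invitations and the gift-card draw, not for sending surveys.
- **Sub-study.** Participants "will be asked to wear an accelerometer for 7-day periods at baseline and every month for 6 months (i.e., 7 different occasions" and have research appointments. The poster in Appendix 7 also places lifestyle and cardiovascular-risk questions at these visits.
- **Analysis.** Protocol (Statistics) and SAP name one-way repeated measures ANOVA or a Mann-Whitney test over these occasions. Neither has a rule for missing surveys.

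**The concern.** If the prompt is the only trigger for a survey, a participant who no longer opens the App is no longer asked for the outcome. Loss to follow-up then depends on exposure, and probably on benefit too, since people who find the App unhelpful have the most reason to drop it.

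Three features of the design make this matter:

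1. There is no comparison group. The result is a within-person change, so selective loss enters the estimate directly.
2. The loss cannot be modelled by App use. Appendix 6 says the Flurry data are aggregate and not linked to individuals, so the researchers would not know who had stopped.
3. Loss is plausible on the plan's own terms. Eight surveys of 30–45 minutes amount to 4–6 hours, rewarded by a draw for ten $20 gift cards.

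At stake are the large study's own question about physical activity over six months and, outside the sub-study, all the evidence on cardiovascular risk.

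**Working it through.** **Who is exposed.** If all 60 sub-study members come from the 300, then 300 − 60 = 240 have no staff visits. Trial design, item 2 also allows recruitment by advertisement. Each sub-study member who does not come from the 300 raises the 240 by one.

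**Is there a plan figure to reproduce?** No. Neither document gives an App retention or survey response rate. The only allowance for loss is in the sub-study, where 60 are recruited against a stated need of 44 (1 − 44/60 = 26.7%). That group has visits, so the figure does not carry over. Everything below rests on assumed values.

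**Possible size.** Let p be the share still using the App at six months, g their mean change and s the mean change in people who stop. Assume every persistent user responds and nobody who stopped does.

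- Mean over all enrolled: T = p·g + (1 − p)·s
- Mean observed: O = g
- With s = 0: O/T = 1/p
- With s = g/2: O/T = 2/(1 + p)
- With s = g: O/T = 1, no bias

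| Assumed p | Responders of 240 | O/T if s = 0 | O/T if s = g/2 |
|---|---|---|---|
| 70% | 168 | 1/0.7 = 1.43 | 2/1.7 = 1.18 |
| 50% | 120 | 1/0.5 = 2.00 | 2/1.5 = 1.33 |
| 30% | 72 | 1/0.3 = 3.33 | 2/1.3 = 1.54 |

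The ratios are free of units. This matters because the Godin questionnaire gives a score in arbitrary units. The 20 min/week target in the sample size section belongs to moderate-vigorous activity in the sub-study and should not be carried across.

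**Could a gain appear where there is none?** Suppose the true mean change is zero, and change correlates with persistence (as a normal liability) at c. Responders then show a mean change of c·φ(z)/p standard deviations of change, with z the normal quantile for 1 − p.

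- p = 80%: φ(z)/p = 0.35, so 0.035 to 0.105 SD for c = 0.1 to 0.3
- p = 60%: φ(z)/p = 0.644, so 0.064 to 0.193 SD
- p = 40%: φ(z)/p = 0.966, so 0.097 to 0.290 SD

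**Complete cases.** If the ANOVA keeps only people with all seven follow-up surveys, and response is independent across occasions at 95%, 90% or 80%, then 240 × 0.95⁷ = 168, 240 × 0.90⁷ = 115 or 240 × 0.80⁷ = 50 remain.

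**The case against.** The strongest reply is that the Protocol does not call the prompt the sole route. The surveys sit at ordinary web links, e-mail addresses are held for tracking, and the flow chart and consent pages, which might describe contact, are not in the text available. This stands as far as feasibility goes: another route is open. But no document commits the team to using it, and a team following the written procedure would not.

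Several stronger readings are tempting, and the documents do not support them:

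- *The primary result is compromised.* The Protocol's primary outcome is moderate-vigorous activity in the 60, who have monthly accelerometer wear and appointments. It is not described as depending on the prompt. The SAP's primary outcome is breaks in sedentary time at one month, with no instrument named. It would be exposed only if taken from the Workplace Sitting Breaks Questionnaire.
- *The six-month result describes only persistent users.* Someone may answer a prompt while hardly using the App, and sub-study members can be reached at visits.
- *The bias is certainly upward.* This depends on how stopping relates to change, which is unknown. If those who stop change as much as the rest, there is no bias.
- *Loss of non-users would create a rise from month to month.* A complete-case repeated measures ANOVA uses the same people throughout, so changing composition cannot do this. Selection would still shift the overall level of change.
- *No analysis could help.* People who stop late leave earlier surveys behind, so models and sensitivity analyses can use them. They could bound the bias but not remove it.

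**Conclusion.** The point holds for questionnaire outcomes in large-study participants outside the sub-study. Followed as written, the procedure links outcome collection to continued App use in an uncontrolled design and describes no fallback. Changes up to six months in self-reported activity and cardiovascular risk are therefore likely to over-represent persistent users.

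The size cannot be stated from the documents. The factors of 1.4, 2.0 and 3.3 assume 70%, 50% and 30% persistence, no gain in people who stop, and response only from persistent users. They shrink to 1.2, 1.3 and 1.5 if people who stop gain half as much. This is an inexpensive improvement to make before follow-up starts, because an outcome not sought at month six cannot be recovered later.

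**What to change.** 1. In Large study procedures, state: *Each survey link will be e-mailed at its scheduled time to every enrolled participant, whether or not the App is still in use, with one reminder. The prompt in the App remains as a second route.*
2. Add an item to each follow-up survey: *Are you still using the App? If not, when did you stop?* Individual use is not otherwise known.
3. State in Protocol and SAP that people who stopped using the App remain in follow-up and in the six-month analysis. Report response at each occasion by App use, and name the handling of missing surveys with a sensitivity analysis that varies the assumed change in non-responders.
4. Reconcile this with Anonymity or Confidentiality, which says that identifying details stay on the device and do not reach the researchers, whereas Participant recruitment collects e-mail addresses, dates of birth and initials.

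Cost: a short amendment and wording in the consent form (not available here) that e-mail will carry survey links. Addresses and links already exist. The estimated change will probably be smaller, but it will come closer to describing everyone who enrolled.

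### Participants harmed by taking part are excluded from the study, and neither document continues their measurement or follows the adverse effect; the bias is probably small and of uncertain sign

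*Protocol*

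**What the plan says.** The rule is in the protocol's Assessment of Safety section. Its trigger reads "Should any participant experience adverse effects as a consequence of participation in the study", and its consequence is that "they will be excluded from the study and receive routine clinical care". No grade or severity is required. For serious events and deaths the section adds that they will be "reviewed by the medical monitor within 24 hrs of becoming aware of events", and then: "Any Serious Adverse Events will be reported to the University of Manitoba Health Ethics Boards and St. Boniface Hospital". It gives no further measurement and no follow-up to resolution for any event.

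The rule is imposed by the study. It is distinct from the participant's own right to leave, which the Informed consent section covers.

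The measurements at stake are those under Study procedures: surveys on eight occasions for everyone, and, for the Winnipeg sub-study, participants "will be asked to wear an accelerometer for 7-day periods at baseline and every month for 6 months". The protocol's primary outcome is the change in moderate-vigorous physical activity (MVPA) in the 60 sub-study participants. The SAP's primary outcome is breaks in sedentary time from baseline to 1 month. Neither the protocol's Statistics section nor the SAP says how missing data or data after exclusion are handled, or who is analysed.

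**The concern.** Stopping an activity that has hurt someone is good care. Ending observation of that person is a separate decision, and the plan makes both at once. By the rule's own wording the people removed are those for whom the intervention went badly, so their loss is not a random thinning of the sample.

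The result is a before/after change in one group, with no comparison arm in which similar losses could be seen. If the excluded would have changed less than the rest (an injured person who becomes less active, say), the gain is overstated. If they were the keenest users and would have gained more, it is understated.

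Safety information is lost as well. Beyond review and reporting of serious events, the study does not observe how an adverse effect develops after the person is excluded.

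**Working it through.** **Inputs from the protocol's Sample Size section:** MVPA 72 ± 64 min/week before and 92 ± 86 after, so a planned gain of 20; pre/post correlation r = 0.8, with 0.5 used there for total activity; 60 recruited.

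**Assumed, because the documents give no rate and no outcome for those harmed:** 1 to 3 of 60 excluded before the final measurement; their mean change c between -20 and 40 min/week; true mean gain over all 60 equal to 20.

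**The plan's own figure.** SD of change = √(64² + 86² - 2 × 0.8 × 64 × 86) = √2685.6 = 51.82. A two-sided 5% test with 80% power for a gain of 20 then needs 53 participants (normal approximation) or 55 (t), not the stated 44. That is a separate matter. Only the SDs and the planned gain are used below.

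**Bias formula.** Let p be the share excluded. The overall mean satisfies 20 = (1 - p) × observed + p × c. Hence bias = observed - 20 = p(20 - c)/(1 - p).

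| Excluded | c = -20 | c = 0 | c = 20 | c = 40 |
|---|---|---|---|---|
| 1 of 60 | +0.68 | +0.34 | 0 | -0.34 |
| 3 of 60 | +2.11 | +1.05 | 0 | -1.05 |

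All entries are in min/week. Example: 3 of 60 with c = -20 gives 0.05 × 40/0.95 = 2.11.

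**Against the standard error.** With 57 remaining, SE = 51.82/√57 = 6.86. Then 2.11/6.86 = 0.31 and -1.05/6.86 = -0.15. At r = 0.5 the SD of change is √5988 = 77.38 and the SE is 10.25, so the largest bias is 2.11/10.25 = 0.21 SE.

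**Outside the assumed range.**
- 6 of 60 with c = -20: 0.10 × 40/0.90 = 4.44 min/week. With SE = 51.82/√54 = 7.05, this is 0.63 SE.
- 3 of 60 with c = -72 (all mean baseline activity lost): 0.05 × 92/0.95 = 4.84 min/week, or 4.84/6.86 = 0.71 SE.

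**False positives.** If the true mean change were 0 and the excluded fell by 20, the bias would be +0.34 (1 of 60) or +1.05 (3 of 60). The two-sided 5% test would then reject in 5.03% or 5.26% of studies.

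**The SAP's 1-month primary.** The documents give no SD for breaks, so the bias is expressed per SD by which the excluded differ from the overall mean: q/(1 - q), with q the share excluded by month 1. Only exclusions in the first month count. If 1 to 3 of 60 exclusions are spread evenly over six months, q = p/6 and the bias is 0.003 to 0.008 SD. If all fall in month 1, q = p and it is 0.017 to 0.053 SD.

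**The case against.** The strongest objection is that this is immaterial. The Risk and Benefits section calls the risk minimal, the eligibility section says "Participants will be healthy volunteers able to provide informed consent", and the trigger is limited to effects caused by taking part. On the assumed range the bias is under a third of a standard error and the false-positive rate barely moves. That stands, and it keeps the point minor. It does not remove it: the number excluded depends on how staff read a rule with no threshold, and the loss of safety follow-up does not depend on the size of the bias.

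A second objection is that recruiting 60 already allows for dropout. Extra recruits restore precision; they do not correct loss that is related to outcome. It is also fair to say that a control group would not by itself cure informative loss, and that ordinary dropout is probably the larger source of missing data.

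A third is burden. Asking someone who has been hurt for further 30 to 45 minute surveys and 7-day wear periods is a judgement for the ethics board. That stands too, so the requests must be voluntary.

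Some stronger readings are tempting but unsupported:
- A reader might infer that data already collected are discarded. The text does not say so. A complete-case repeated measures ANOVA could drop a person's earlier visits, but that would come from the analysis method, not from the safety rule.
- A reader might infer that excluded people lose the App and with it the survey prompt, since "Research participants will be prompted within the App to a hyperlink to complete the research questionnaires on Survey Monkey". The safety section does not say they stop using the App, and the App is publicly available whether or not a person is enrolled.
- A reader might infer that the rule inflates the effect. The direction depends on how the excluded would have changed, which the documents do not tell us.

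**Conclusion.** The point holds as a minor one. Followed as written, the plan stops observing participants because the intervention harmed them, and nothing in either document restores their later outcome data or the course of the effect.

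The bias is probably small: about -1.1 to +2.1 min/week of MVPA, or -0.15 to +0.31 SE at r = 0.8. This rests on the assumed 1 to 3 exclusions in 60, a mean change of -20 to 40 in those people and a true gain of 20. A reader might take that range as a ceiling, or infer that many exclusions are needed before the bias matters. Neither follows: three people who lost all their baseline activity would shift the estimate by 4.8 min/week (0.71 SE). That is an extreme case, not an expected one, but it means no firm threshold can be given.

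**What to change.** **Protocol, Assessment of Safety.** Reword so that participants with adverse effects from participation stop App activities as clinically needed and receive routine clinical care; data already collected are kept; remaining surveys and accelerometer wear periods are still requested unless the person declines or withdraws; and the adverse effect, serious or not, is followed until it resolves or month 6. For anyone no longer using the App, send survey links by e-mail. The Participant recruitment section already states that "we will be asking for their e-mail addresses".

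**SAP.** Keep these participants in the analysis with all their available data, for example with a mixed model for repeated measures in place of a complete-case repeated measures ANOVA. The model makes use of incomplete records; it does not replace continued measurement, which is what addresses loss related to outcome. Report how many stopped the App and how many left follow-up, with reasons.

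**Cost.** A few sentences in each document, an ethics amendment approved before implementation (as the Ethics section requires) and a line in the consent form. For an early event the burden is up to seven surveys (1 week and months 1 to 6) and, in the sub-study, six wear periods per affected person, all voluntary.
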